SECONDARY JUDGMENTS CRITERION	1) To assess the criteria to be taken into account to establish a diagnostic score, the number of patients per collected variable will be determined according to the diagnosis of GCA confirmed or not. 2) The number of positive TAB will make it possible to calculate the rate of "positive TAB" in the "negative" CDU group. The frequency of vasculitis lesions of the vasa vasorum (VVV) and/or periadventitial vessels (VPA) will be established in this "negative" CDU group. Patients in the GCA group diagnosed by CDU will be compared to the group of GCA patients diagnosed by TAB for clinical and biological data. 3) The description of the evolution of the halos at W3/W4 will make it possible to study whether there is any correlation with the rate of corticosteroid-dependent patients, the number of relapses, ischemic complications, etc... 4) The number of TAB slide reading discrepancies will be established, and its corollary, the number of inter-operator discrepancies on the echo-Doppler. 5) Diagnostic costs (consultation and/or hospitalization, CDU and TAB), induced costs (complication, adverse event of TAB), avoided costs (absence of TAB for CDU positive patients), and indicators of efficacy (positive diagnosis rate according to the CDU, according to the diagnostic algorithm (CDU +/- TAB), number of Horton's disease successfully treated at 2 years of follow-up and the number of patients for whom the surgery could be avoided) will be determined.
METHODOLOGY / DIAGRAM OF THE STUDY	Diagnostic study in internal medicine, cross-sectional, prospective, regional multicenter.
SUBJECT INCLUSION CRITERIA	-Patient cared for in one of the participating centres: ≥ 50 years CRP supehigher Tolaboratory normal Suspects of GCA deend with: 
 o Patients suspected of GCA according to the expert clinician and/or o Aortitis or arteritis of one or more arteries originating from the aorta on imaging (angio-CT, angio-MRI or PET-CT18FDG) Benote Security Social or in benoteficant by the intermediary of a third person having given their participation agreement by understanding and accepting the constraints of the study

	
Free subject, without guardianship or curatorship or subordination

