NUMBER OF PATIENTS	The objective is to include at least 100 patients carrying a Horton. It is therefore planned to include 168 people suspected of having gigantocellular arteritis.
LENGTH OF SEARCH	
Duration of the inclusion period: 2 years
 
Duration of participation of each subject: 2 years
 
Data analysis duration: 6 months
 
Total duration of the study: 4 years and 6 months

STATISTICS	
Analysis of the primary endpoint will consist of determining the positive predictive value of CDU and the algorithm will be considered valid in the absence of alternative diagnoses within 2 years of follow-up in the group considered to have GCA on a clinical-biological suspicion + "positive" echo-Doppler.
 
To establish a probability model of the clinical and paraclinical score calculation type, the variables significantly associated with the diagnosis will be determined by logistic regression. A number of points will be assigned to each variable based on the strength of its association with the diagnosis. The area under the ROC curve will be used as an indicator of the discriminative power of the score.
 
Correlation analyzes will be carried out to study a possible link between the description of the halos and the persistence of a poorer clinical response and to assess the inter-operator reproducibility for the reading of the TAB slides and CDUs performed in 1st intention.

EXPECTED BENEFITS	The objective is to validate the diagnostic algorithm using CDU in 1st intention to confirm cases of GCA. The remaining place of the

temporal artery biopsy will be specified. A predictive model including the result of the CDU will be proposed and will aim, after validation on other populations, to modulate the ACR score. This result will have a major impact in the daily practice of hundreds of doctors and patients per year in France, and will allow a reduction in the diagnostic delay.

2. Scientific justification and general description of the research

2.1- Rationale for the study

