- 4) Determine inter-observer variability/concordance for pathology and echo-Doppler examination.
- 5) Describe the cost-result of the algorithm

4. Research design

4.1-Precise statement of the main evaluation criteria and, where applicable, the secondary evaluation criteria

4.1.1-Main evaluation criterion

The number of patients with an alternative diagnosis in the 2 years of follow-up among patients considered to have GCA on clinical and biological suspicion + "positive" echo-Doppler.

4.1.2-Secondary evaluation criterion(ies)

- 1) To assess the criteria to be taken into account to establish a diagnostic score, the number of patients per collected variable will be determined according to the diagnosis of GCA confirmed or not.
- 2) The number of positive TAB will make it possible to calculate the rate of "positive TAB" in the "negative" CDU group. The frequency of vasculitis lesions of the vasa vasorum (VVV) and/or periadventitial vessels (VPA) will be established in this "negative" CDU group. Patients in the GCA group diagnosed by CDU will be compared to the group of GCA patients diagnosed by TAB for clinical and biological data.
- 3) The description of the evolution of the halos at W3/W4 will make it possible to study whether there is any correlation with the rate of corticosteroid-dependent patients, the number of relapses, ischemic complications, etc...
- 4) The number of TAB slide reading discrepancies will be established, and its corollary, the number of inter-operator discrepancies on the echo-Doppler.
- 5) Diagnostic costs (consultation and/or hospitalization, CDU and TAB), induced costs (complication, adverse event of TAB), avoided costs (absence of TAB for CDU positive patients), and indicators of efficacy (positive diagnosis rate according to the CDU, according to the diagnostic algorithm (CDU +/- TAB), number of Horton's disease successfully treated at 2 years of follow-up and the number of patients for whom the surgery could be avoided) will be determined.

4.2-Description of the research methodology

4.2.1-Experimental plan

Diagnostic study in internal medicine, cross-sectional, prospective, regional multicenter.

4.2.2-Procedure of the study

4.2.2.1-Inclusion

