- On the anapat voucher will be indicated the name of the protocol (ECHORTON), if the corticosteroid treatment was initiated and if so its start date.
- Fixing the biopsy specimen with 10% buffered formalin
- Measurement of the size of the fixed transmitted arterial segment
- Paraffin inclusion after salami every 3-4mm
- Staining with Hematoxylin Eosin Saffron (HES)
- Unsystematic Orcein or Van Gieson staining

- Preparation of numerous slides (thickness 3 µm) 8 levels until the block is exhausted
- Research :
 - o inflammatory infiltrate, granuloma, giant cells (location of this infiltrate intima, media, adventitia)
 - o of necrosis
 - o fibrosis
 - o calcification (location to be specified)
 - o thickening of the intima
 - o rupture, duplication of the internal elastic limit
 - o vasa vasorum (VVV) lesion
 - o lesion of vasculitis of the periadventitial vessels (VPA)
 - o thrombosis
 - o possible lesions of arteriosclerosis
 - o possible amyloidosis lesion (Red-Congo not systematic)
 - o Conclusion: GCA yes/no/doubtful/other
- Forwarding for proofreading of all the slides by an expert pathologist blind to the diagnosis retained by the initial pathologist: CHU de Poitiers

Collection of systematic adverse effects (at V3)

4.4- Expected duration of people's participation and description of the timing and duration of all periods of the trial, including follow-up, if applicable

Duration of inclusion: 24 months

Total duration of participation in the study for the patient: 24 months

Duration of analyses: 6 months

Estimated study duration: 54 months

From the first inclusion, the person in charge must immediately inform the competent authority and the CPP of the actual start date of the study.

The study end date will be sent by the person in charge to the CPP within 90 days. The end date of the research corresponds to the term of the participation of the last person who agrees to the research, or if applicable, to the term defined in the protocol.

4.5- Description of permanent or temporary stoppage rules

4.5.1- Termination of a person's participation in research

Subjects may withdraw their non-objection and request to leave the study at any time and for any reason.

In the event of premature discharge, the invigilator should document the reasons as fully as possible.

In the event of a lost subject, the supervisor will make every effort to reconnect with the person.

4.5.6- Stopping part or all of the search

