- Benefiting from enhanced protection, namely persons deprived of their liberty by a judicial or administrative decision, persons staying in a health or social establishment, adults under legal protection, and finally patients in an emergency situation.
- Patient participating in another clinical trial.
- Pregnant or breastfeeding women, women of childbearing age who do not have effective contraception (hormonal/mechanical: oral, injectable, transcutaneous, implantable, intrauterine device, or surgical: tubal ligation, hysterectomy, total oophorectomy)

5.3- Recruitment methods

Patients followed in the internal medicine department of the participating centers and suspected of having giant cell arteritis will be offered to participate in the study.

5.4- Procedure for premature termination of research or exclusion of a person from research and procedure for monitoring the person

The withdrawal of a patient from the study will in no way change his usual care in relation to his illness. In the event of an adverse event, whether serious or not, precise monitoring may be considered depending on the seriousness of the adverse event and the severity. In the context of a withdrawal of non-objection, the data collected will not be used in accordance with the patient's wishes.

6- Safety assessment

6.1- Procedures put in place for the recording and notification of adverse events

The occurrence of an Adverse Effect related to the treatment of the patient during this protocol will give rise to a declaration in the appropriate vigilance system (pharmacovigilance, biovigilance, haemovigilance, materiovigilance, etc.).

6.2- Supervisory Committee

Not planned.

7.- Statistics

7.1- Description of planned statistical methods, including schedule of planned interim analyzes

All the parameters collected will be presented in tables and diagrams containing descriptive statistics for each of the sub-populations (confirmation or not of GCA), as well as for the entire population analyzed, according to the following methods:

- for the quantitative variables: the number of missing values and non-missing values, the mean, the standard deviation, the 95% confidence interval, the median, the 1st quartile, the 3rd quartile, the minimum and the maximum,
- for qualitative variables: the number of missing values and non-missing values, frequencies, percentages and 95% confidence intervals, for each of the modalities of the variable.

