The analysis of the primary endpoint will consist of determining the positive predictive value of CDU and the algorithm will be considered valid in the absence of an alternative diagnosis within 2 years of follow-up in the group considered to have GCA. on a clinical-biological suspicion + "positive" echo-Doppler.

To establish a probability model of the clinical and paraclinical score calculation type, the variables significantly associated with the diagnosis will be determined by logistic regression. A number of points will be assigned to each variable based on the strength of its association with the diagnosis. The area under the ROC curve will be used as an indicator of the discriminative power of the score.

Correlation analyzes will be carried out to study a possible link between the description of the halos and the persistence of a poorer clinical response and to evaluate the inter-operator reproducibility for the reading of the TAB slides and Doppler echo images.

The analysis of diagnostic costs, induced costs, avoided costs, and efficiency indicators will make it possible to determine the costs/results of the diagnostic algorithm.

7.2- Expected number of people to be included in the research, and expected number of people in each research location with its statistical justification

According to a retrospective study of 42 patients treated for suspected Horton's disease, 70% of them had their Horton's diagnosis confirmed. To include at least 100 patients with Horton's disease over the study period, it is therefore necessary to include at least 142 patients suspected of Horton's disease (100 confirmed Horton's/42 other diagnoses). To take into account the possible overestimation of confirmed cases of Horton's disease due to biases of the retrospective study, the objective is to include 168 patients suspected of Horton's disease.

The population over 50 represents just over one million inhabitants in Charente-Maritime, Deux-Sèvres and Vienne. Considering an incidence of 1.2/10,000 inhabitants, approximately 120 new cases of Horton are detected each year.

Department	Number of people over 50	Number of new cases of Horton per year	Number of new Horton cases over 24 months	Estimation of the number of suspected cases of Horton over 24 months
Charente Maritime	491 871	59	118	168
Vienna	284,078	34	68	97
Two Sevres	261 272	31	63	90
Total	1037221	124	249	355

Table 2: theoretical recruitment potential

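### Reader concordance (objective 4) is to be evaluated by an unspecified correlation, which measures association; no chance-corrected agreement measure is planned for the biopsy and Doppler readings

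*Combined protocol and SAP*

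**What the plan says.** Section 3.2, objective 4: "Determine inter-observer variability/concordance for pathology and echo-Doppler examination". This is a question about agreement.

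The matching criterion, in section 4.1.2 and the summary, is a count: "The number of TAB slide reading discrepancies will be established, and its corollary, the number of inter-operator discrepancies on the echo-Doppler".

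Section 7.1 opens with a general rule for every qualitative variable: "frequencies, percentages and 95% confidence intervals, for each of the modalities of the variable". Applied to discrepancies, this would give a discrepancy rate with a confidence interval.

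The only method that 7.1 ties to reproducibility comes later, in a sentence that starts "Correlation analyzes will be carried out to study a possible link between the description of the halos" and continues "to evaluate the inter-operator reproducibility for the reading of the TAB slides and Doppler echo images". One word, correlation, therefore covers both a genuine association question (halo against clinical response) and an agreement question. The summary has the same construction, but its CDU part is limited to first-line examinations: "to assess the inter-operator reproducibility for the reading of the TAB slides and CDUs performed in 1st intention". No coefficient is named in either place. Neither kappa nor any other chance-corrected measure appears anywhere in the document.

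The TAB reading ends in four labels (section 4.3.4): "Conclusion: GCA yes/no/doubtful/other". All slides are re-read by an expert blind to the initial diagnosis (4.3.4), the images of CDU n°1 and n°2 are reviewed blind by one expert (4.3.2), and both sets of results go into the e-CRF (4.6).

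**The concern.** A correlation coefficient asks whether two readings move together. Concordance asks whether they are the same. If the expert consistently calls 'doubtful' what the local pathologist calls 'no', the readings can stay strongly correlated while many of them differ.

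The TAB scale adds a second difficulty. A coefficient computed on yes/no/doubtful/other needs the labels in an order. The plan gives none, and 'other' has no natural place in one.

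At stake is how objective 4 is reported. A correlation presented as reproducibility could be read as agreement, and the coefficient and coding could be chosen after the readings are known. The protocol's own rationale treats pathology variability as not negligible and CDU as operator-dependent, so readers will look at this result.

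**Working it through.** The documents contain no reading data and no agreement figure, so there is nothing to reproduce. Every table below is an assumption used to show behaviour; none is a prediction.

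**Scale of the illustration.** Planned inclusion is 168, with at least 100 GCA cases (7.2). Take CDU sensitivity 69% and specificity 100% (from the retrospective series in 2.1), with every CDU-negative patient biopsied (4.2.2.2).
- CDU-positive: 100 × 0.69 = 69.
- Biopsies: 168 − 69 = 99.
- GCA missed by CDU: 100 − 69 = 31. Calling all 31 'yes' on TAB is a maximum, since 2.1 itself gives 20 to 30% negative biopsies.
- Non-GCA: 168 − 100 = 68, all read 'no' locally.

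**Assumed table.** Of the 68 local 'no' slides, the expert reads 34 as 'no' and 34 as 'doubtful'. All 31 'yes' slides agree. Code no = 0, doubtful = 1, yes = 2, with x local and y expert. Then n = 99, Σx = 62, Σy = 96, Σx² = 124, Σy² = 158, Σxy = 124.

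- Raw agreement: (34 + 31)/99 = 65/99 = 66% (Wilson 95% CI 56 to 74%).
- Pearson r: (99×124 − 62×96) / √[(99×124 − 62²)(99×158 − 96²)] = 6324/√(8432×6426) = 0.86.
- Quadratic kappa: 2×6324 / [8432 + 6426 + (96 − 62)²] = 12648/16014 = 0.79. The term (96 − 62)² is the penalty for the shift between readers; r has no such term.
- Unweighted kappa: chance agreement = (68×34 + 31×31)/99² = 3273/9801 = 0.334; kappa = (0.657 − 0.334)/(1 − 0.334) = 0.48.

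The part of the gap due to the shift and to unequal spread is 0.86 against 0.79. Most of the remaining distance to 0.48 comes from weighting: quadratic weights treat a one-step difference as mild, while unweighted kappa treats it as a full disagreement.

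**Dependence on coefficient and table.** With 72 biopsies (sensitivity 96%, the highest value in 2.1: 168 − 96 = 72, 4 'yes'), let 17 of 68 'no' slides be re-read as 'doubtful'. Pearson r is 0.69 and Spearman 0.50, against quadratic kappa 0.61 and raw agreement 76%. Spearman here falls below both.

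**Binary CDU result.** With two categories Pearson r is phi. Over all one-directional disagreement tables with n = 168, phi exceeds kappa by at most 0.135. That maximum occurs at cells 6/44/0/118: phi = 6×118/√(50×118×6×162) = 0.296, kappa 0.161. With 20 one-sided discrepancies (80/20/0/68), phi is 0.79 and kappa 0.76.

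**Why a count alone is not enough, and why kappa alone is not either.** Two assumed yes/not-yes tables with about 90% raw agreement:

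| Cells | Raw agreement | Chance agreement | Kappa | Positive agreement | Negative agreement |
|---|---|---|---|---|---|
| 26/5/5/63 | 89/99 = 90% | 0.570 | 0.77 | 52/62 = 84% | 126/136 = 93% |
| 1/3/4/64 | 65/72 = 90% | 0.883 | 0.17 (95% CI −0.21 to 0.55) | 2/9 = 22% | 128/135 = 95% |

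The same discrepancy rate can hide very different agreement on positives. This matters because biopsies come only from CDU-negative patients, so positives may be few.

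**The case against.** The best defence is that the declared criterion is itself a direct measure of disagreement. The general rule in 7.1 would present it with a confidence interval, and the readings are blinded and recorded. Gross disagreement would be seen. This stands, and it is the main reason the point is minor. A reader might infer that the plan does not measure agreement at all; the discrepancy count shows otherwise.

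Second, no coefficient is named and the text is a translation. An absolute-agreement intraclass correlation does penalise a shift, so 'correlation' is not bound to mean Pearson. This also stands. The defect is an unspecified statistic whose usual meaning does not answer the question. The wording needs settling under either reading.

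Third, it is tempting to conclude that correlation will make agreement look better than it is. The 72-biopsy table shows that this is not general. Nor is it true that r equals quadratic kappa whenever there is no shift. In an assumed table with rows 20/20/0, 0/19/0 and 0/20/20, both readers have the same mean, yet r is 0.71 and quadratic kappa 0.67, because their spreads differ.

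Fourth, a reader might infer that 4.3.2 plainly counts doubtful CDU examinations as negative and so contradicts objective 2, which names a doubtful group. The line in 4.3.2 is too unclear for that: the items listed under it could define either term. It needs clarifying but is not a proven contradiction.

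Finally, kappa depends on prevalence. That is correct, and it argues for reporting kappa beside other measures, not for correlation.

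**Conclusion.** The point holds in limited form. Objective 4 asks for concordance; beyond a discrepancy count, the plan names only an unspecified correlation and no chance-corrected measure. The mismatch matters most for the four-category TAB conclusion. In the assumed 99-biopsy table it is the difference between r 0.86 and quadratic kappa 0.79, unweighted kappa 0.48 or raw agreement 66%. For a binary CDU result it is small. These figures rest on Pearson r, an assumed order no < doubtful < yes, an assumed one-way re-reading of half the 'no' slides, and the maximum number of positive biopsies. Other choices change both size and direction. Severity is minor: this is a secondary objective, and neither the primary endpoint nor the sample size is affected.

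**What to change.** In 7.1 and the summary, keep correlation only for halo persistence against clinical response. For reproducibility, state that the following will be reported:

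1. The two-way table of local against expert reading.
2. Percent agreement with 95% CI. This is the complement of the discrepancy rate, which stays the declared criterion.
3. Cohen's kappa with 95% CI: unweighted over the TAB categories, and for CDU on positive versus not positive, the split that routes patients to biopsy in 4.2.2.2.
4. Positive and negative agreement beside each kappa (for TAB, yes versus not yes).

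Also state whether the CDU n°2 re-readings are included: 4.3.2 plans them, the summary confines the analysis to first-line examinations, and 7.1 sets no limit. Reconcile whether doubtful is a separate CDU level; if it is, show the three-level table as well.

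The cost is a few sentences and no new data. Two drawbacks should be acknowledged in the report: kappa will be unstable if positive biopsies are few, and a pooled kappa mixes local readers from six centres.

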- diagnostic profitability: its sensitivity is imperfect with globally 20 to 30% of negative results. This result is partly due to the segmental and focal vascular tropism of the disease and to the existence of a more "proximal" form exclusively involving the aorta and its large trunks, but also to the difficulty of pathological diagnosis with an inter-observer variability not negligible (specimen size, number of cuts, doctor's experience, consideration of VVV and VPA (11-13). Thus, the result of the biopsy does not often influence the action to be taken by the practitioner (14) .

As a result, research over the past 20 years has aimed to develop alternative diagnostic means to TAB. This has notably been the case with color Doppler ultrasound since the description by Wolfgang A. Schmidt and collaborators of the halo sign on the superficial temporal arteries in 1995 (15).

Color Doppler ultrasound of ATS, subject to certain technical conditions (detailed later) and an experienced operator, is a non-invasive tool, at least as sensitive and very specific for the diagnosis of GCA as have shown well by recent studies and meta-analyses (16-18). A very recent study even showed a higher sensitivity of CDU compared to TAB for the diagnosis of GCA, 96% versus 67% for an identical specificity (119). CDU can additionally analyze other arterial segments potentially affected by disease. Thus the diagnostic performance of the CDU is further increased if the analysis concerns in addition to the ATS, the subclavian, axillary and common carotid arteries. (20).

Within the framework of a retrospective and monocentric study on the CH of La Rochelle (LR) we found results similar to those published with a sensitivity of 69% and a specificity of 100% of the CDU among 20 patients all suspected of 'GCA' (13).

From critical reading of the scientific literature and our experience, we believe that the specificity problem of CDU becomes negligible if the pre-test probability is high, if systemic necrotic vasculitis has been ruled out, if the operator is experienced and if the CDU positivity criteria are strictly defined (example: certain and bilateral character of the Halo, hypoechoic character of the halo, not taking into account the effects of stenosis on the ATS).

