Knowing that the diagnosis of GCA is difficult, the majority of patients likely to be carriers of Horton are referred to clinicians. However, to account for patients not cared for by monitors participating in the study and patients refusing to participate, the goal is to include 45-50% of suspected Horton cases.

Center	Recruitment objective (Nb patients/month)	Duration of inclusion (months)	Forecast over the entire duration of the study
La Rochelle	2	24	48
Rochefort	1.5	24	36
Poitiers	2	24	48
Niort	1.5	24	36
Angouleme	1	24	24
Nantes	2	12	24

Table 3: goal of inclusion

7.3- Expected degree of statistical significance

The statistical tests will be carried out at the bilateral alpha risk of 5%.

7.4- Statistical criteria for stopping research

An interim analysis at 1 year of the start of inclusions will be made. Depending on the results (absence or presence of an alternative diagnosis in the group considered to have GCA on a clinical-biological suspicion + "positive" echo-Doppler) the study will be continued or not.

7.5- Method for taking into account missing, unused or invalid data

In case of premature termination and non-compliance with the protocol, the reasons will be documented. Missing data will be described in terms of numbers and corresponding percentages for each criterion and at each visit. There are no plans to replace patients exiting the study.

Patients suspected of Horton's disease are treated with corticosteroids. The administration of this treatment requires regular dose reviews. Patients are therefore monitored regularly in current practice and few loss of follow-up are expected in the study. On the other hand, cortisone treatment allows a good clinical evolution in patients with gigantocellular arteritis and the response to treatment in the very old subject seems comparable to that of the younger subject. The expected death rate is therefore that of the general population of the same age. Thus, if less than 5% of the patients in the study are lost to follow-up or died, the missing data will be replaced by deductive imputation when possible (e.g. patients with a combination of clinical signs, biological and examinations in favor of a horton and a good evolution under corticosteroids will be classified as suffering from Horton's disease). In the event of a higher rate of missing data, other methods of managing problematic data will be considered.

7.6- Management of modifications made to the analysis plan of the initial strategy

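### Does the 12-month look in section 7.4 put the PPV estimate and the secondary objectives at risk by allowing a stop on one alternative diagnosis?

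*Combined protocol and SAP*

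**What the plan says.** Section 7.4 is the only statement on early stopping: "An interim analysis at 1 year of the start of inclusions will be made". That places one look halfway through the 24-month inclusion period in section 4.4. The input is the "absence or presence of an alternative diagnosis in the group considered to have GCA" on clinical and laboratory suspicion plus a positive Doppler, and the outcome is that "the study will be continued or not". It gives no direction, no count, no decision-maker, and no statement on whether a stop would end inclusion only or follow-up as well. Section 6.2 plans no supervisory committee.

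Section 7.1 has two parts that bear on this. One concerns estimation: "The analysis of the primary endpoint will consist of determining the positive predictive value of CDU". The other is a decision rule: "the algorithm will be considered valid in the absence of an alternative diagnosis within 2 years of follow-up".

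Section 7.2 sizes the study by headcount: "To include at least 100 patients with Horton's disease over the study period", with a retrospective series in which "70% of them had their Horton's diagnosis confirmed". Section 4.4 sets 24 months of participation for each patient.

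**The concern.** A criterion phrased as presence or absence is most naturally read as a stop on the first case. A study whose ultrasound is very good but not perfect could then end halfway through recruitment. The verdict of non-validity would be correct, but the study also promises a PPV and five secondary objectives (score model, biopsy yield, halo evolution, reader agreement, cost), and these keep their value when the PPV is, say, 98%.

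Stopping at the look would leave about 50 patients with giant cell arteritis, or 84 with the fastest accrual and 70% confirmed, against the stated 100. Follow-up at that moment would be at most 12 months. If enrolled patients were then released, none would have the two-year verification that defines the endpoint in section 4.1.1. The early stop would therefore fall on the case where a precise estimate is most useful.

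**Working it through.** **The plan's own size.** 100 / 0.70 = 142.9, against 142 stated. The increase to 168 is by judgement and implies 100 / 168 = 59.5% confirmed.

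**Accrual at 12 months** (section 7.2, Table 3)
- Even accrual to 168: 84, or 50.0%.
- Five centres without Nantes: 8 per month × 12 = 96, or 57.1%.
- All six centres, with Nantes active throughout year 1: 10 per month × 12 = 120, or 71.4%.

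Table 3 sums to 216, not 168. On that base, 96 to 120 is 44% to 56%. The table does not say in which 12 months Nantes recruits, so 120 is a corner case.

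**Ultrasound-positive patients at the look** = accrued × confirmed share × sensitivity. The protocol projects no such number. As an assumption I use the sensitivities cited in section 2.1: 69% from the local series of 20, and 96% from a published series.
- 84 × 0.595 × 0.69 to 0.96 = 35 to 48
- 84 × 0.70 × 0.69 to 0.96 = 41 to 56
- 120 × 0.70 × 0.96 = 81 (fastest corner)

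**Precision lost by stopping on one case.** Exact (Clopper-Pearson) 95% intervals for the PPV; full size is taken at about the same observed error rate.

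| Stopped | Interval, % | Width | Full size | Width | Difference |
|---|---|---|---|---|---|
| 1/35 | 85.1–99.9 | 14.8 | 2/69 | 9.7 | 5.1 |
| 1/48 | 88.9–99.9 | 11.0 | 2/96 | 7.1 | 3.9 |
| 1/41 | 87.1–99.9 | 12.8 | 2/81 | 8.3 | 4.5 |
| 1/56 | 90.4–99.95 | 9.5 | 2/113 | 6.0 | 3.5 |
| 1/81 | 93.3–99.97 | 6.7 | 2/113 | 6.0 | 0.7 |

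If no second case would have appeared, the loss is larger: 1/35 against 1/69 is 14.8 − 7.8 = 7.0 points, 1/48 against 1/96 is 11.0 − 5.6 = 5.4, and 1/81 against 1/113 is 6.7 − 4.8 = 1.9.

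**Chance that the look shows at least one case** = 1 − [1 − (1 − PPV) × f]^n, where f is the share of alternative diagnoses already apparent. With uniform entry over 12 months, f = 0.25 if they emerge evenly over 24 months and f = 1 if they emerge at once. Neither the PPV nor the timing is in the documents.

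| PPV | n = 35 to 48 | n = 81 |
|---|---|---|
| 100% | 0% | 0% |
| 99.5% | 4–21% | 10–33% |
| 99% | 8–38% | 18–56% |
| 98% | 16–62% | 33–80% |
| 95% | 36–92% | 64–98% |

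The local series ("a sensitivity of 69% and a specificity of 100% of the CDU among 20 patients") would imply the first row. The table says little beyond the PPV one chooses to assume.

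**Effect on the verdict.** Under section 7.1, one case gives not valid at 12 months and at the end alike. No case at the look only lets the study continue, on the reading that presence is the stopping result. That reading gives no route to a false declaration of validity and no alpha to protect.

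**The case for a change.** The strongest case for a change is that section 7.4 is incomplete on any reading. If presence means stop, the rule can cut off a useful PPV estimate. If the decision is discretionary, a section headed as statistical stopping criteria contains none. A single paragraph would settle the direction, the decision-maker and the follow-up of enrolled patients, with no patients beyond the 168. The gap matters more because ultrasound-positive patients are not biopsied (section 4.2.2.2), so this look is the only planned formal review of misdiagnosis.

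What stands is that the wording is unclear and that an interval running from 85% to nearly 100% is a poor estimate of a PPV. What does not stand is that the plan contains a harmful rule. The present text lets the sponsor continue after one case. Loss of follow-up is a worst case that no section prescribes: section 4.4 sets 24 months per patient, and section 7.5 describes regular monitoring in current practice, although section 4.5.6 leaves premature termination open. A rule against stopping on one case would also remove an early exit in a study with no committee. Replacing the present wording by a criterion for the sponsor to fix later would put one unspecified rule in place of another.

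**Conclusion.** The plan can stay as it is. A stop on one case, if the sponsor chose it, would be a futility stop consistent with section 7.1: the validity question would already be answered, and correctly. Going on would buy 48 to 84 further inclusions (168 − 120 to 168 − 84) and a PPV interval narrower by about 1 to 5 points at the same observed error rate, or up to 7 points if no further case arose. It would also give more data for the secondary objectives; that gain is not quantified here beyond the patient counts. With no stated precision target and a 60k€ budget (section 13.1), reasonable statisticians could decide either way. A reader who wants a PPV of 97% to 98% to count as success is in truth objecting to the zero-case criterion in section 7.1, which is a separate matter.

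The silence on follow-up after a stop is one that analysts would fill from section 4.4 by keeping enrolled patients to 24 months. The sizes above depend on the assumed sensitivities of 69% to 96%, a confirmed share of 59.5% to 70%, and Table 3 accrual; the trigger probabilities depend on an assumed PPV and timing. The conclusion that the verdict cannot be distorted depends on none of these, only on presence being the stopping result.
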